**Diagnosis and Main Criteria for Inclusion/Exclusion (Continued):**

**Inclusion (Continued):**

5. Subject has an Eastern Cooperative Oncology Group (ECOG) performance score of 0 to 1.
6. Subject must be  $\geq 18$  years of age.
7. Subject must have adequate hematologic, renal and hepatic function as follows:
  - Bone Marrow: Absolute neutrophil count ANC  $\geq 1,500/\text{mm}^3$  ( $1.5 \times 10^9/\text{L}$ ); White blood cells  $\geq 3,000/\text{mm}^3$  ( $3 \times 10^9/\text{L}$ ); Platelets  $\geq 100,000/\text{mm}^3$  ( $100 \times 10^9/\text{L}$ ); Hemoglobin  $\geq 9$  g/dL (5.58 mmol/L)
  - Renal function: creatinine  $\leq$  ULN or if creatinine  $>$  ULN calculated creatinine clearance via the Cockcroft Gault formula of  $\geq 50$  mL/min
  - Hepatic function:
    - Aspartate aminotransferase (AST) and alanine aminotransferase (ALT)  $\leq 2.5 \times$  upper limits of normal (ULN). For subjects with liver metastases, AST and ALT  $\leq 5 \times$  ULN;
    - Bilirubin:  $\leq 1.5 \times$  ULN; for subjects with Gilbert's syndrome bilirubin  $> 1.5 \times$  ULN is allowed if no symptoms of compromised liver function are present.
8. Subject must be able to swallow pills.
9. Female and male patients of fertile age, and/or their partners should use contraception. If male, subject and subject's female partner(s) of childbearing potential must follow the contraception recommendations as described in Section 5.2.4. If female, subject must be either postmenopausal for at least 1 year, surgically sterile (bilateral tubal ligation, bilateral oophorectomy or hysterectomy), or the subject and the subject's male partner(s) must follow the contraception recommendations as described in Section 5.2.4.  
Female subjects must have negative results for pregnancy tests performed:
  - Screening on a serum specimen obtained within 7 days prior to initial study drug administration, and
  - prior to dosing on a urine sample obtained C1D-2 unless the serum pregnancy test was collected within 7 days of C1D-2.
10. Must voluntarily sign and date each informed consent, approved by an Independent Ethics Committee (IEC)/Institutional Review Board (IRB), prior to the initiation of any screening or study specific procedures.

**Exclusion:**

1. Phase 1 ONLY: Subject has had any prior anti-cancer therapy other than:
  - Hormonal, non-myelosuppressive, biologic, targeted, or immune therapy (must be completed  $\geq 4$  weeks prior to Cycle 1 Day -2).
  - One line of cytotoxic chemotherapy (must be completed  $\geq 4$  weeks prior to Cycle 1 Day -2).
  - Adjuvant/neoadjuvant radiotherapy (must be completed  $\geq 12$  months prior to Cycle 1 Day -2, with field not involving  $> 10\%$  of bone marrow reserve).
  - Tumor lesion irradiation with intent of symptom palliation  $\geq 4$  weeks prior Cycle 1 Day -2.

**Diagnosis and Main Criteria for Inclusion/Exclusion (Continued):**

**Exclusion (Continued):**

2. Phase 2 ONLY: Subject has had any prior chemotherapy, radiotherapy, investigational anti-cancer agents or biologic therapy for the disease under study. Single non-target lesion irradiation with intent of symptom palliation is allowed if  $\geq 2$  weeks prior Cycle 1 Day -2.
3. Subject has known hypersensitivity to etoposide, platinum compounds or veliparib.
4. Phase 1 ONLY: Subject has received prior myelopoietic growth factors.
5. Subject has current central nervous system (CNS) or leptomeningeal metastases or history of CNS or leptomeningeal metastases. If CNS metastasis is suspected, a head CT should be performed at screening.
6. Subject has a history of seizures within 12 months of Cycle 1 Day -2 or diagnosed neurological condition placing subject at the increased risk of seizures.
7. Subject has received traditional herbal anti-cancer medicine (e.g., Chinese, Asian etc.) within 14 days prior to Cycle 1 Day -2.
8. Subject has had major surgery within 6 weeks prior to Cycle 1 Day -2 (subjects must have completely recovered from any previous surgery prior to Cycle 1 Day -2).
9. Subject has clinically significant and uncontrolled major medical condition(s) including but not limited to:
  - Uncontrolled nausea/vomiting/diarrhea;
  - Active uncontrolled infection;
  - History of hepatitis B (HBV) with surface antigen (HBsAg) positivity within 3 months prior to the date of informed consent for this study (if HBsAg status is unknown it must be tested at screening);
  - History of hepatitis C (HCV) with HCV RNA positivity within 3 months prior to the date of informed consent for this study (if HCV RNA status is unknown it must be tested at screening);
  - Symptomatic congestive heart failure (New York Heart Association [NYHA] class  $\geq$  II);
  - Unstable angina pectoris or cardiac arrhythmia;
  - Psychiatric illness/social situation that would limit compliance with study requirements;
  - Any other medical condition, which in the opinion of the Investigator, places the subject at an unacceptably high risk for toxicities.
10. Subject is pregnant or lactating.
11. The subject has a history of another active cancer within the past 3 years except cervical cancer in situ, in situ carcinoma of the bladder, squamous or basal cell carcinoma of the skin or another in situ cancer that is considered cured by the investigator (e.g., in situ prostate cancer, breast ductal carcinoma in situ [DCIS]).

Questions regarding the eligibility of individual subjects should be directed to the AbbVie TA MD.

Investigational Products: Doses: Mode of Administration:	Veliparib Phase 1 Dose Escalation cohorts: 80, 120, 160, 200 and 240 mg BID (higher doses up to 400 mg BID may be tested) Phase 2 Randomized Double-Blind arms: 240 mg BID Continuous monotherapy maintenance: 400 mg BID Oral
Investigational Products: Doses: Mode of Administration:	Placebo – BID Phase 2 ONLY Combination therapy: matching capsules for 240 mg BID Continuous monotherapy maintenance: matching capsules for 400 mg BID Oral
Reference Therapy: Doses: Mode of Administration:	Carboplatin AUC 5 mg/mL*min Intravenous infusion
Reference Therapy: Doses: Mode of Administration:	Etoposide 100 mg/m  Intravenous infusion
Duration of Treatment: Subject will remain on study drug until disease progression or unacceptable toxicity.	
Criteria for Evaluation: Efficacy: 
 Progression-free survival (PFS) will be derived according to disease progression (radiographic progression per RECIST version 1.1) or death. Radiographic tumor assessments for response will be conducted by CT scanning at baseline, every 6 weeks from C1D-2 for the first 24 weeks (Phase 1) or 30 weeks (Phase 2), then every 9 weeks until disease progression.         
 
 Objective response rate (ORR) will be derived per RECIST version 1.1. Radiographic tumor assessments for response will be conducted by CT scanning at baseline, every 6 weeks from C1D-2 for the first 24 weeks (Phase 1) or 30 weeks (Phase 2), then every 9 weeks until disease progression.         
 
 Duration of overall response (DOR) will be derived according to disease progression (radiographic progression per RECIST version 1.1).         
 
 Overall survival will be determined by the Investigator at assessments throughout therapy. After the final visit, survival information will be collected via electronic data capture (EDC) at 2 month intervals (or as requested by sponsor to support data analysis).         
 
 ECOG performance status will be determined by the Investigator at each assessment.         
 Pharmacokinetic: Blood samples for pharmacokinetics of veliparib, carboplatin (Phase 1 Dose Escalation only) and etoposide (Phase 1 Dose Escalation only) will be collected at designated time points throughout the study. Pharmacokinetics of veliparib and etoposide will be assessed to determine the drug-drug interactions. In addition, pharmacokinetics of carboplatin will be determined.	

**Criteria for Evaluation (Continued):**

**Pharmacodynamic:**

Research to find biomarkers that may be predictive of veliparib activity will be conducted. Serum, plasma, blood and archived tissue samples will be collected at designated time points throughout the study.

**Pharmacogenetic:**

DNA samples may be analyzed for genetic factors contributing to the subject's response to veliparib, or other study treatment, in terms of pharmacokinetics, efficacy, tolerability and safety.

**Safety:**

Adverse events, laboratory profiles, physical examinations, vital signs and neurological assessments will be evaluated and recorded throughout the study.

**Statistical Methods:**

**Efficacy:**

The following end point will be analyzed using data obtained from subjects in Phase 1 and Phase 2 separately:

**Objective Response Rate**

The proportion of subjects with objective response (CR or PR) as assessed by the investigator using RECIST 1.1 will be calculated for all dosed subjects.

The following end point will be analyzed using data obtained from subjects in Phase 2:

**Progression-Free Survival**

Progression-Free Survival will be defined as the number of days from the date of randomization to the date of earliest radiographic disease progression or death. All disease progression will be included regardless whether the event occurred while the subject was taking study drug or had previously discontinued study drug. If the subject does not experience disease progression or death, then the data will be censored at the date of the last radiographic disease assessment.

**Overall Survival**

Overall survival will be defined as the number of days from the date of randomization to the date of death. For subjects who did not die, their data will be censored at the date of last study visit or the last known date to be alive, whichever is later.

**Duration of Overall Response**

Duration of overall response will be defined as the number of days from the date of first response (CR or PR) to the earliest documentation of radiographic progressive disease. If a subject is still responding, then the subject's data will be censored at the date of the subject's last available radiographic disease assessment. For subjects who never experience response, the subject's data will not be included in the analysis.

**Performance Status**

Changes and/or percent changes from baseline will be summarized using descriptive statistics for each scheduled post-baseline visit and for the Final Visit for ECOG performance status. Post-baseline measurements more than 30 days after the last dose of study drug will not be included. Subjects that do not have a baseline measurement or do not have any post-baseline measurements will not be included.

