- To evaluate if veliparib in combination with carboplatin and etoposide followed by placebo monotherapy results in improved duration of overall response (DOR) versus placebo in combination with carboplatin and etoposide followed by placebo monotherapy.
- To compare PFS and OS of subjects treated with veliparib in combination with carboplatin and etoposide followed by veliparib maintenance to PFS and OS of subjects treated with veliparib in combination with carboplatin and etoposide followed by placebo maintenance.
- To evaluate performance status.

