### **5.3.3.2 Definition of Disease Progression**

Disease progression will be defined as radiographic progression of disease as determined by the investigator by RECIST (Version 1.1) [Appendix C](#).

Clinical progression as determined by the investigator, which may be characterized as, but not limited to:

- Increase in at least two points of ECOG performance status attributable to cancer progression;
- Subject requires non-palliative radiation, chemotherapy or surgery due to progressive disease;
- Death from progressive disease.

In cases where an Investigator determines that a subject has met the criteria for clinical disease progression, every effort should be made to confirm the progression radiographically.

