#### **8.1.5.4 ECOG Performance Status**

Changes and/or percent changes from baseline in ECOG performance status will be summarized using descriptive statistics for each scheduled post-baseline visit and for the final visit. Post-baseline measurements more than 30 days after the last dose of study drug will not be included. Subjects that do not have a baseline measurement or do not have any post-baseline measurements will not be included. Changes and/or percent changes from baseline to each visit will be compared between Arm A and Arm C as well as between Arm B and Arm C using an analysis of covariance with treatment arm as the factor and baseline value as a covariate.

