#### **10.6.4 ECOG Performance Status (Arm A vs Arm C and Arm B vs Arm C)**

Mean Change (80% CI) from baseline to each scheduled post-baseline visit (as defined in [Table 2](#)) will be compared between Arm A and Arm C as well as between Arm B and Arm C using ANCOVA with treatment arm as a factor and baseline ECOG value as a covariate.

Subjects that do not have a baseline measurement or do not have any post-baseline measurements will not be included. Post-baseline measurements will be excluded after 30 days of the last dose of veliparib/placebo (including both combination period and maintenance period), carboplatin, or etoposide, whichever occurs the last.

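### The visit-by-visit ECOG comparison has no rule for death and drops values more than 30 days after the last dose, so it compares differently selected subjects and largely misses a benefit that acts by delaying progression or death (tertiary endpoint, low priority)

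*Protocol*

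**What the plan says.** Protocol Section 4.0 lists as a tertiary objective "To evaluate performance status". The Synopsis, under Performance Status, plans a description: "Changes and/or percent changes from baseline will be summarized using descriptive statistics for each scheduled post-baseline visit and for the Final Visit". Section 8.1.5.4 makes this more than a description: "Changes and/or percent changes from baseline to each visit will be compared between Arm A and Arm C", and likewise for Arm B and Arm C, by analysis of covariance. SAP 10.6.4 keeps the comparison of mean change at each visit, "using ANCOVA with treatment arm as a factor and baseline ECOG value as a covariate".

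Both documents restrict the data in the same two ways.
- Subjects with no baseline or no post-baseline ECOG are left out.
- Late values are left out. The Protocol says "Post-baseline measurements more than 30 days after the last dose of study drug will not be included". The SAP counts from the last dose of whichever study drug stops last.

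The surrounding text matters too.
- Protocol Table 8 schedules ECOG at screening, Cycle 1 Day -2, Day 1 of each later cycle, the Final Visit and the 30-Day Follow-Up Visit. None is scheduled in Post-Treatment Follow-Up or Survival Follow-Up.
- Under Protocol 5.4.1, the Final Visit is the one at which progression is identified or another discontinuation criterion is met.
- SAP Section 6.0 defines a Final Value as the last non-missing value up to 30 days after the last dose. SAP Table 2, to which 10.6.4 refers for its visits, has a row for it.
- The scale in Protocol 5.3.1.1 runs from 0 to 4 and has no grade for death. Neither document gives a rule for death or dropout in this analysis.

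**The concern.** Study treatment stops at progression, and a dead subject has no ECOG value. A visit-wise mean therefore describes subjects who are alive, have a post-baseline value and are within 30 days of their last dose. If veliparib delays progression as the sample-size section assumes, that group shrinks faster in Arm C than in Arm A, and the groups compared at later visits are no longer the randomized ones. The arm that loses more deteriorating subjects need not look worse.

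What is at stake is a stated objective. In a trial whose primary endpoint is PFS, later deterioration is a natural way for benefit to show in performance status, and it is the part this analysis sees least.

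**Working it through.** **1. The plan's own figure.** Inputs from Protocol 8.2 and SAP 4.3: Arm C median PFS 5.5 months, hazard ratio 0.63 (A vs C) and 0.75 (B vs C), one-sided alpha 0.1, 80% power, 60 per arm. Schoenfeld events = 4(1.2816 + 0.8416)² / (ln 0.63)² = 4 × 4.508 / 0.2135 = 84.5, so 85, as stated; power at 85 events is 0.802. No effect size, SD or power is given for ECOG.

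**2. Who is left at each visit.** With exponential PFS, Arm C share = 0.5^(t/5.5), Arm A share = that^0.63 and Arm B share = that^0.75.
- Week 24 (5.52 months): C 0.499, A 0.645, B 0.594. Out of 60: 29.9, 38.7, 35.6.
- Week 36 (8.28 months): C 0.352, A 0.518, B 0.457. Out of 60: 21.1, 31.1, 27.4.

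These are progression-free counts. Stopping early for toxicity lowers the number on treatment, and the 30-day window adds some recent stoppers back.

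**3. Which subjects and values are lost.**
- Death before Cycle 2 Day 1 with no Final Visit: no post-baseline value, so the subject leaves the analysis, although SAP 5.1 defines ITT as all randomized subjects.
- Stopping for toxicity with later progression: under Post-Treatment Follow-Up (Protocol 5.3.1.1) the Final Visit comes at progression. Its ECOG is discarded if that is more than 30 days after the last dose.
- The 30-Day Follow-Up Visit is only approximately 30 days after the last dose, so a day-31 value is lost.

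**4. Benefit acting only through PFS (A vs C, hazard ratio 0.63).** Assumptions not in the documents: 15% of PFS events are deaths; baseline ECOG is 1 in 60%; ECOG worsens by 1–2 points starting up to 1.5, 3 or 6 weeks before the PFS event; visits every 3 weeks; random ±1 error at 20% of visits, or fewer; follow-up varied. One-sided 0.1:

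| Analysis | Power |
|---|---|
| Visit-wise ANCOVA, Weeks 12–36 (difference 0.01–0.05 points) | 12–18% |
| Final Value ANCOVA | 36–60% |
| Time to increase of at least 2 points, or death | 53–75% |
| Time to increase of at least 1 point, or death | 38–71% |

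The Final Value result depends on data maturity. With near-complete follow-up it fell to 16–19%, because most subjects in both arms then contribute the value taken at progression, however long that was delayed. The 1-point threshold is sensitive to visit-to-visit error: at about 85 events its power was 38–42% with error at 20% of visits and 65–72% at 5%.

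A second model (+1 point at progression, median 4 months from progression to death) gives the same picture at month 6: visit-wise difference 0.00 with rejection 12%; last value including the progression visit -0.13 with 39%.

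**5. A direct effect on ECOG while on treatment.** In the second model with hazard ratio 1 and a latent effect of 0.3 points (about 0.2 after rounding and the floor at 0), visit-wise power is 66%, 55% and 43% at months 3, 6 and 9. By formula at month 6 (28 in C, 37 in A), with an assumed SD of 0.7, the smallest difference detectable with 80% power is 2.1232 × 0.7 × √(1/28 + 1/37) = 0.37 points; for SD 0.5 to 1.0 it is 0.27 to 0.53.

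**The case against.** The strongest reply is that the plan already looks beyond subjects on treatment. Values up to 30 days after the last dose count, ECOG is taken at the visit where progression is identified, and the Final Value row keeps one value for everyone with a post-baseline ECOG in the window. This stands. A reader might infer that ECOG is compared only in subjects still on treatment, and that any real difference is almost undetectable. The documents do not support either: the Final Value comparison has moderate power at the planned event count, and step 5 shows that a direct difference can be detected. The low figure belongs to the visit-wise rows and to a benefit acting through progression or death.

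A reader might also infer that early toxic deaths would go unseen. They would not. Deaths count in PFS and OS (SAP 10.3), in the summaries of adverse events leading to death and of deaths (SAP 11.2 and 11.3), and in the DMC's review (SAP 14.1.3). They are missing only from the ECOG analysis.

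Percent change, undefined for a baseline of 0, remains in the Protocol as an and/or option, but SAP 10.6.4 has already dropped it.

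Two objections to the remedy also have force. In step 4 worsening arises only around the PFS event, so time to worsening or death partly re-tests PFS, and its power should not be expected to reach the 80% planned for PFS. And no ECOG is scheduled after the Final and 30-Day visits, so counting every later death while censoring survivors at their last ECOG would be informative censoring.

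**Conclusion.** The concern holds in a limited form. The visit-wise ANCOVA has no rule for death or dropout, and under the PFS difference the plan assumes it compares differently selected subjects. It then retains little of a benefit that acts by delaying progression or death: about 12–18% power against a nominal 10%. The Final Value comparison recovers part of this, but it varies with data maturity and still omits deaths and late values.

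The counts in step 2 rest on the plan's own medians and hazard ratios. Every power figure for ECOG rests on assumed ECOG behaviour and applies to A vs C; the assumed effect for B vs C is smaller (0.75). The endpoint is tertiary, lies outside the hierarchy in SAP Table 5 and carries no power claim. The point is a cheap improvement of low priority and does not touch the primary conclusion.

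**What to change.** In SAP 10.6.4, for A vs C and B vs C in the ITT population:
- Add time from randomization to the first ECOG increase over baseline of at least 2 points, or death, with the LDH-stratified log-rank test and Cox model already planned for PFS. Protocol 5.3.3.2 already uses this size of change: "Increase in at least two points of ECOG performance status attributable to cancer progression"; the new endpoint would not require attribution. With entry limited to ECOG 0 or 1, every subject can reach it on the 0–4 scale. The 2-point threshold should lead because it is less exposed to transient fluctuation.
- Use Final Visit and 30-Day Follow-Up values regardless of days since the last dose.
- Censor living subjects at their last ECOG. Count a death only if it falls within a stated gap after the last ECOG, as SAP 10.3 does for PFS after missed assessments. Count all deaths in a sensitivity analysis.
- Present the visit means as descriptive, with numbers contributing and cumulative deaths by arm at each visit.

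The cost is one SAP paragraph and one table, from data already collected. The remaining weakness is that some censoring stays informative because ECOG collection ends with the Final and 30-Day visits; the sensitivity analysis shows how much that matters.

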**Statistical Methods (Continued):**

**Pharmacokinetic:**

Plasma concentrations of veliparib, etoposide, and carboplatin and pharmacokinetic parameter values will be tabulated for each subject and each dose level, and summary statistics will be computed for each sampling time and each parameter.

The effects of co-administration of veliparib on etoposide pharmacokinetics will be addressed by analyzing the Cycle 1 Day 1 (veliparib with carboplatin and etoposide) and Cycle 2 Day 1 (carboplatin and etoposide alone) etoposide pharmacokinetic variables, including  $T_{max}$ , dose normalized  $C_{max}$  and dose normalized AUC.

**Pharmacodynamic:**

Biomarker results will be tabulated for each subject and each regimen, and summary statistics will be computed for each sampling time and each parameter. The relationship between biomarker status and clinical outcome or drug exposure may be examined.

**Safety:**

- The safety of veliparib in combination with carboplatin/etoposide will be assessed by evaluating the study drugs exposure, adverse events, serious adverse events, all deaths, as well as changes in laboratory determinations and vital sign parameters. Safety will be summarized per dose level using descriptive statistics for the dose escalation cohorts and per treatment arm in Phase 2.
- RPTD was determined based on the rate of DLTs and overall tolerability of the combination of veliparib, carboplatin and etoposide with at least 9 subjects treated at the RPTD in Phase 1 and will be further evaluated in Phase 2.

